#### 12.6. REVIEW OF CONCOMITANT MEDICATIONS (ANTIPLATELETS/ANTICOAGULANTS) DUPLEX ULTRASOUND (DUS) ASSESSMENT

Lower extremity arterial duplex ultrasonography is widely accepted as a method of determining arterial stenosis. Duplex ultrasonography combines spectral Doppler Technology in addition to B-mode imaging to allow the visualization of blood flow patterns within the arteries and veins. This spectral Doppler also provides a method to measure the velocity of the blood flow at specific locations.

The peak systolic blood flow velocity within the Tacks as well as the target vessel will be taken to determine the peak systolic velocity ratio (PSVR). All scheduled and unscheduled DUS exams shall be reviewed by an independent core laboratory for analysis.

The DUS exam should be performed on all subjects at the 30-day, 6, and 12 month follow-up visits. Duplex ultrasonography and/or angiography should be performed prior to any endovascular intervention during the follow-up period in order to assess the treated vessel patency. Operators should have experience with DUS and the specific methods for calculating the blood flow velocities. Operators will be trained on the DUS protocol provided by the respective core laboratory. Each operator is required to submit a test case DUS exam to the core lab prior to performing any study-required DUS exams.

A comprehensive overview for DUS acquisition requirements can be found in the core laboratory manual.

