**Table 7 - Primary Patency at 1 Year in LEVANT 2 for ITT Completers**

Measure	Test Drug-Coated Balloon (DCB) %(n/N) [95% CI]	Control PTA %(n/N) [95% CI]
Primary Patency	65.2% (172/264) [59.4, 70.9]	52.6% (71/135) [44.2, 61.0]

The performance goal for TOBA II is derived from the lower limit of the 95% confidence interval for the Test DCB and Control PTA in Levant 2 given that the expectation is that the Tack

device will resolve dissections without negatively impacting primary patency at 12 months. The primary patency rate is dependent on the type of balloon used and therefore the performance goal will be calculated using the Levant 2 lower 95% confidence limits and the proportion of subjects enrolled and treated with DCB ( $p_{DCB}$ ) and Control PTA ( $p_{PTA}$ ) in the TOBA II Trial. The following formula will be used:

$$PG = p_{DCB} \times 59\% + p_{PTA} \times 44\%$$

For example, assuming the proportion of subjects meeting the ITT definition in TOBA II is 60% DCB and 40% Control PTA, the calculated performance goal will be  $0.6 \times 59\% + 0.4 \times 44\% = 53\%$ . The primary efficacy performance goal will be calculated upon completion of the index procedure for all enrolled subjects (see **Section 16.4**).

*Sample Size Rationale:* The sample size required to have data evaluable for the primary efficacy endpoint at 12 months, was calculated using PASS 2012, a one-sample Exact Test, power = 90%, one-sided Type I error controlled at 2.5%, and setting the maximum proportion of subjects treated with DCB enrolled at 60%. In this case, the performance goal for primary patency at 12 month is 53%. A current estimate for primary patency at 12 months in the TOBA European trial (POBA use only) is 75%. Conservatively, the primary patency for DCB + Tack and Control PTA + Tack was assumed to be 65% for the purpose of the sample size calculation. Using those assumptions, 178 subjects are required to have data evaluable for the primary efficacy endpoint at 12 months.

The power at N=178 subjects is provided in **Table 8** varying the assumed proportion of subjects treated with DCB + Tack. As can be seen in **Table 8**, the sample size calculation for the TOBA II trial has at least 90% power given the proportion of subjects treated with DCB + Tack is 60% or less.

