**Table 8 - Power for N=178 Subjects Varying the Proportion of Subjects Treated with DCB + Tack Meeting the ITT Definition with Data Available to Evaluate the Primary Efficacy Endpoint at 12 months**

Proportion of Subjects Meeting ITT Definition with Tack +		Performance Goal a	Assumed Patency at 12M for TOBA II			Power at N=178
DCB	Control PTA		DCB + Tack	Control PTA + Tack	Pooled	
30%	70%	49%	65%	65%	65%	99.1%
40%	60%	50%				98.0%
50%	50%	52%				92.4%
60%	40%	53%				90.0%

aThe performance goal, PG, is calculated as PG = proportion DCB + Tack\*59 + proportion control PTA + Tack\*44.

*Primary Statistical Analysis:* The primary statistical analysis will be conducted in subjects who meet the ITT definition and have data evaluable for the primary efficacy endpoint. Subjects with a missing DUS ultrasound at 12 months and a patent DUS ultrasound at a later visit with no intervening clinically driven TLR will be considered patent at 12 months. In the event an angiogram is available within the 12 month visit window, the angiographic core-lab determined stenosis using the 50% cutoff will be used instead of the DUS core-lab determined stenosis. The primary statistical method is a one-sample exact test comparing the proportion of subjects with

primary patency to the performance goal using a one-sided  $\alpha = 0.025$ . The exact two-sided 95% confidence interval for the proportion of subjects with primary patency will be calculated.

The primary patency proportion will be calculated such that the numerator is the number of subjects who are patent at 12 months with no clinically-driven TLR by the close of the 12 month visit window. The denominator is the total number of subjects with a core-lab adjudicated DUS ultrasound finding of either patent or not patent at 12 months, clinically-driven TLR prior to the close of the 12 month visit window, or missing 12 month DUS with a patent DUS finding at a subsequent visit with no intervening clinically driven TLR.

*Additional Analysis:* If pooling is not justified per the methods outlined in **Section 16.5**, the additional analyses specified in that section will be completed. If there is missing data for the ITT subjects, the sensitivity to missing data analysis outlined in **Section 16.6** will be completed. Additionally, the primary statistical analysis will be conducted in the per protocol sample.

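### Section 16.9 lets a late duplex scan into the primary patency analysis only if it is patent; any bias is expected to be upward, and its size depends on a number of late scans that the plan does not give

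*Combined protocol and SAP*

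**What the plan says.** The Primary Statistical Analysis text of Section 16.9 has two sentences on this point.

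- The imputation sentence says that a subject whose 12-month DUS is missing and who has "a patent DUS ultrasound at a later visit with no intervening clinically driven TLR will be considered patent at 12 months".
- The denominator sentence lists three ways in: a core-lab 12-month DUS finding, whether patent or not; a CD-TLR before the 12-month window closes; or "missing 12 month DUS with a patent DUS finding at a subsequent visit with no intervening clinically driven TLR".

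Section 16.6 speaks more broadly of imputing from an earlier or later DUS or angiogram, but leaves the detail to the primary analysis text. It also plans best-case, worst-case and tipping-point analyses, as sensitivity analyses only.

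On scheduling, Section 12.6 says: "The DUS exam should be performed on all subjects at the 30-day, 6, and 12 month follow-up visits". Table 5 shows no DUS at 24 or 36 months. Beyond the scheduled visits, DUS appears only under unscheduled visits, when clinically indicated or per standard of care.

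**The concern.** The first route into the denominator accepts either DUS result, while the third accepts only a success. For a subject with no 12-month DUS and no CD-TLR by window close, a late patent scan adds one to both numerator and denominator, and a late non-patent scan adds nothing to either. The outcome decides whether the subject is analysed.

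This is a single-arm test against a fixed performance goal, so there is no control arm in which such a selection could cancel. What is at stake is the one-sided 2.5% error rate of the primary efficacy test and the patency estimate that goes with it.

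**Working it through.** **Inputs from the plan (Section 16.9).** One-sample exact test, one-sided α = 0.025, performance goal 53% at 60% drug-coated balloon use. True patency for power "was assumed to be 65% for the purpose of the sample size calculation". On that basis, "178 subjects are required to have data evaluable for the primary efficacy endpoint at 12 months".

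**Step 1: reproduce the plan's figure.** The smallest r with P(X ≥ r | 178, 0.53) ≤ 0.025 is r = 108, with tail probability 0.0237 (r = 107 gives 0.0335). Power is P(X ≥ 108 | 178, 0.65) = 0.9004. Table 8 states 90.0%, so the plan's figure reproduces.

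**Step 2: classify subjects with no 12-month DUS and no qualifying angiogram.**

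| Situation | Treatment in 16.9 |
|---|---|
| CD-TLR before window close | failure, in denominator |
| Later DUS patent, no intervening CD-TLR | success, in denominator |
| Later DUS not patent, no CD-TLR by window close | in neither |
| No later DUS, no CD-TLR by window close | in neither |

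**Step 3: false-pass rate.** Assumptions: true in-window patency is 53%; 178 subjects have either a 12-month result or a late exam; L of them have a late exam, patent with probability q. Both L and q are assumed, because the documents give neither.

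Let X ~ Bin(178 − L, 0.53) and Y ~ Bin(L, q). The rule analyses (X + Y)/(178 − L + Y). With c(n) the exact critical value at n, the false-pass rate is Σ over y of P(Y = y) × P(X ≥ c(178 − L + y) − y).

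| L | Apparent patency, q = 0.53 | False pass, q = 0.53 | q = 0.40 | q = 0.25 |
|---|---|---|---|---|
| 1 | 53.1% | 2.4% | 2.3% | 2.1% |
| 2 | 53.3% | 2.5% | 2.4% | 2.3% |
| 5 | 53.7% | 3.1% | 2.8% | 2.4% |
| 10 | 54.4% | 4.6% | 3.9% | 3.2% |
| 20 | 56.0% | 9.8% | 7.0% | 4.7% |

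For example, at L = 10 and q = 0.53 the apparent patency is (168 × 0.53 + 5.3)/(168 + 5.3) = 94.34/173.3 = 54.4%.

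Comparators at q = 0.53: counting late exams by their result gives 2.4% at every L, since X + Y is then Bin(178, 0.53). Using no late exam gives 1.7% to 2.3% for the L shown. Adding the late exams to 178 in-window results, instead of placing them inside the 178, changes little: 3.3%, 4.7% and 9.2% for L = 5, 10 and 20.

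**Step 4: what is held fixed matters.** The q = 0.25 column keeps in-window patency at 53%. If overall patency is held at 53% instead, in-window patency must be (94.34 − 1.25)/173 = 53.8% at L = 5 and (94.34 − 2.5)/168 = 54.7% at L = 10. The false-pass rates are then 3.9% and 7.7%.

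**Step 5: an illustration.** Suppose 106 of 178 are patent on 12-month results: one-sided p = 0.046, a fail. Add ten late exams, five patent and five not. As written, the result is 111/183, p = 0.022, a pass. Counting all ten gives 111/188, p = 0.056, a fail.

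**Step 6: direction.** Every late-imputed subject is a success, so the estimate cannot fall relative to 12-month results alone. Relative to the true rate among all 178, at L = 10 and q = 0.53 the upward bias would vanish only if the late-exam subjects' own 12-month patency were about (178 × 0.544 − 168 × 0.53)/10 ≈ 0.79, against 0.53 in the rest.

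**The case against.** The strongest reply is that the affected group may be nearly empty. A subject must lack a 12-month DUS, have no CD-TLR by window close, and have a later scan that no visit requires. Table 5 also asks sites to repeat a non-diagnostic scan within the visit window. At one or two such subjects the error rate is essentially nominal. This stands, and it limits the size of the point.

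Second, each half of the rule is reasonable for a single scan. A patent scan after 12 months without CD-TLR supports patency at 12 months, whereas a later non-patent scan does not date the restenosis. This also stands, and it is why scoring late non-patent scans as failures would be conservative. It does not justify a denominator that keeps the likely successes and discards the possible failures.

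Third, the worst-case and tipping-point analyses in Section 16.6 would treat the dropped subjects as missing and expose them. That is true, but those analyses do not decide the primary test.

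Fourth, a reader might infer that any 12-month scan done outside the ±30 day window falls under the late rule, which would make the group larger. The text does not settle this. Section 16.9 ties angiograms and CD-TLR to the visit window, but for DUS says only that the finding is at 12 months. A delayed 12-month-visit scan could be read as an ordinary 12-month finding, counted either way.

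**Conclusion.** The asymmetry is explicit in Section 16.9 and nothing elsewhere in the plan corrects it. Any resulting bias in primary patency is expected to be upward. Across the assumptions shown with in-window patency at 53%, the false-pass rate runs from nominal (2.1% to 2.5% for one or two late exams) to between 4.7% and 9.8% for twenty.

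A reader might go further and conclude that the stated 2.5% error rate does not hold. The documents do not support that as an unconditional statement. They give neither the number of late exams nor their patency, and they schedule no DUS after 12 months. Planned attrition of 32 (210 − 178) leaves room for several late exams but does not show that any will occur. Nor do the documents show that late exams would be less often patent than the rest, plausible as that is for clinically indicated scans.

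This should be fixed because the primary test ought not to select subjects on outcome and the correction is cheap. The documents do not establish that the effect will be large.

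**What to change.** Change both the imputation sentence and the denominator sentence of Section 16.9 so that inclusion does not depend on the late result.

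- **Preferred:** use no later DUS in the primary analysis, and move the late-patent rule to the Section 16.6 sensitivity analyses. This avoids calling an undated restenosis a 12-month failure. Cost: a slightly smaller evaluable N.
- **Alternative, conservative:** count a late DUS by its result, patent as success and not patent as failure. Cost: slightly lower observed patency.

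Under either option, align the Section 16.6 wording on earlier or later DUS or angiogram with the chosen rule, and state whether a 12-month scan done outside the ±30 day window counts as a 12-month finding or as missing. No new data or subjects are needed. The choice should be recorded before outcome data are seen, so that it cannot appear to be driven by results.

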#### 16.10. SUBGROUP SUMMARIES FOR PRIMARY ENDPOINTS

Summary statistics for the following subgroups will be summarized. The study was not powered to demonstrate the primary efficacy and safety endpoints within the subgroups and therefore it is not an expectation that the primary safety and efficacy endpoint will be statistically significant within the subgroups

- Gender
- Most severe post-PTA site reported dissection per lesion and the most severe post-PTA core-lab reported dissection per lesion. Additionally the dissection grade may be grouped into two categories defined by the most severe site and corelab reported post-PTA dissection grade reported, i.e. types A-C and types D-F. However, all dissection types per lesion will be recorded in the site and corelab CRFs.
  - The dissection distribution at baseline will be qualitatively compared against the dissection distribution reported in the Levant 2 trial for post-study treatment.
  - The primary efficacy and safety endpoints summarized by worst dissection grade will be qualitatively compared to any and all available relevant data in the literature on outcomes in post-PTA dissection.

#### 16.11. OBSERVATIONAL ENDPOINTS

The observational endpoints are listed in **Section 6.2** and are supportive in nature. Descriptive statistics will be calculated and may be provided in labeling if deemed informative for the user. Descriptive statistics for the purposes of labeling are defined as N, mean, standard deviation, median, interquartile range, minimum and maximum for continuous variables and number and percent of observations for categorical variables.

Standard statistical methods will be used and include the Kaplan-Meier product limit method for time to event endpoints and the Wilcoxon signed rank test for changes from baseline for endpoints compared to baseline. Statistical significance will be defined as two-sided  $\square < 0.05$ . Two sided 95% confidence intervals may be calculated for estimates. P-values and 95% confidence intervals are not intended for the labeling.

Safety endpoints will be evaluated in the sample of subjects meeting the ITT definition only. Efficacy endpoints will be evaluated in both the ITT and PP subjects.

## 17. REGULATORY AND ETHICAL OBLIGATIONS

As the study Sponsor, Intact Vascular is responsible for the overall conduct and quality of the study, including the assurance that the study complies with the regulations and guidance that apply to medical devices evaluated under an Investigational Device Exemption (IDE) and Good Clinical Practice (GCP) guidance (FDA Guidance and ICH E6). Additionally, Intact Vascular will ensure that qualified monitors and designated personnel are monitoring the study and that the Informed Consent process is followed per each site's local and national requirements.

### 17.1. INSTITUTIONAL REVIEW BOARD (IRB) / ETHICS COMMITTEE (EC) APPROVAL

The Principal Investigator at each participating site is responsible for securing IRB/EC approval for this study protocol and the Informed Consent documents. The IRB/EC for each specific institution must review and approve this study protocol, the specific Informed Consent form and any written materials for subjects to be used at that site **prior** to enrollment of the first subject. The Sponsor **must** also review and approve the final Informed Consent documents prior to their use. The Sponsor must receive a copy of any IRB/EC correspondence as well as the final approval letter and the final approved Informed Consent from each IRB/EC. The IRB/EC approval letter must be signed by the IRB/EC chair or designee, identify the IRB/EC name and address, the clinical study protocol by name or number, and the date the approval was granted.

The site investigator is also responsible for initiating and obtaining continuing review of the clinical study. Continuing IRB/EC review and approval should not exceed intervals over one year, but may occur at more frequent intervals as required by site specific IRB/EC policies. The investigator must also provide the Sponsor with all correspondence and documentation of continued IRB/EC approval of the clinical study.

### 17.2. INFORMED CONSENT

All sites shall comply with 21 CFR 50, provisions of ICH Good Clinical Practices (GCPs), local IRB/EC policy and all applicable local regulations for obtaining Informed Consent. Written, informed consent is to be obtained for all subjects prior to treatment as described in **Section 8.3**.

Informed Consent templates will be provided by the Sponsor to all participating clinical sites. Changes to this template made by the site based upon IRB/EC requirements must be provided to the Sponsor for review and approval prior to being submitted to the IRB/EC for review and approval. Any revisions required by a site's IRB/EC should also be provided to the Sponsor for review and approval prior to being submitted to the IRB/EC for final review and approval.

### 17.3. PROTOCOL AMENDMENT AND EMERGENCY DEVIATIONS

Changes to the research conducted under this protocol will be implemented with a formal protocol amendment. Amendments to the protocol may be initiated by the Sponsor or at the request of the Investigator. In either case, changes to the protocol must be approved by the Sponsor and submitted to the applicable regulatory agency as appropriate. A protocol

amendment cannot be implemented at the site without first being signed and acknowledged by the Investigator and approved by the IRB/EC.

Emergency deviations or modifications may be initiated without prior Sponsor or IRB/EC approval only in cases when the deviation is necessary to eliminate an immediate potential hazard to a subject. Emergency deviations or modifications implemented to protect the life or physical well-being of a subject must be reported to the Sponsor and site specific IRB/EC **within 5 business days of occurrence.**

#### 17.4. SUBJECT CONFIDENTIALITY

Confidentiality of subjects will be maintained throughout the study. A unique identification code will be assigned to each subject enrolled into the study. Access to the subject's medical records will be limited to authorized personnel of the Sponsor, their designated monitors, clinical site study staff and authorized regulatory authorities as required by the IRB/EC and/or local or national agencies. Any data that may be published in abstracts or scientific journals and/or presented at medical meetings will reference a unique subject code and will not reveal the subject's identity. The Sponsor and their representatives will make every reasonable effort to protect the confidentiality of the subjects participating in the study.

All U.S. clinical study sites must comply with the provisions of the Health Insurance Portability and Accountability Act (HIPAA) and in accordance with all applicable federal, local and institutional requirements.

### 18. CLINICAL STUDY CONDUCT

#### 18.1. PRINCIPAL INVESTIGATOR AND SITE QUALIFICATION

All Principal Investigator's (PI) and investigational sites will be selected by Intact Vascular through the PI and site qualification process. All selected PI's will be responsible for complying with all study-related and regulatory requirements and will be ultimately responsible for overseeing the conduct of the study at their respective investigational sites, per the Investigator Agreement.

All selected PI's will have the required training and expertise in performing peripheral vascular interventional procedures in a clinical research setting. The investigational sites where the study procedures and assessments are to be performed must have the adequate volume of the target subject population, experienced staff, as well as the appropriate facilities and equipment to meet the requirements of the study protocol and the expected enrollment time frames.

All PI's and research staff must be willing to undergo all study and device-related training and participate and assist with monitoring, audits and inspections initiated by either the Sponsor and/or regulatory authorities.

#### 18.2. PRINCIPAL INVESTIGATOR AND SITE TRAINING

Training of the Investigators and clinical study staff is the responsibility of the Sponsor and their designee. Investigators and study staff will undergo site initiation visit training on the use of the study device, the study protocol, eligibility criteria, and device accountability prior to participating in the study. Training will also include, but is not limited to, instructions on timely and accurate eCRF completion, safety reporting timelines, as well as procedures for acquiring study related images and associated timelines for submission to appropriate core laboratory.

All training of the Investigators and research staff must be documented on the training log before performing any study-related function.

### 18.3. CLINICAL MONITORING

Intact Vascular will designate qualified clinical monitor(s) and oversee the conduct of this study. The clinical monitors will evaluate compliance with the protocol, Good Clinical Practices (FDA Guidance and ICH E6), any specific recommendations made by the site's IRB/EC and the signed Investigator and Study Agreements.

The clinical monitor will conduct periodic monitoring visits to verify that the eCRFs are in agreement with the source documentation and other records, that the rights and well-being of the subjects, and that the trial is being conducted in accordance with the approved protocol/amendments and GCPs. Periodic phone contacts will also be conducted to ensure that the protocol is being followed and to assist the site with queries that may arise.

For record verification purposes during site monitoring visits, the clinical monitor and/or authorized Sponsor representative will be provided access to hospital records, original laboratory data, and other records and data as they relate to the study and as agreed to with the Investigator prior to the initiation of the trial. The Investigator will also make available to the clinical monitor all regulatory documents, all completed eCRFs, informed consent documents, source documentation and other relevant records for all enrolled subjects at the site. It is important that the Investigator and other relevant site personnel are available for consultation with the clinical monitors during the monitoring visits and that sufficient time is devoted at the site to the monitoring process.

If the Sponsor and/or their authorized representative become aware that an Investigator is not complying with the study protocol, the Investigator Agreement, the Declaration of Helsinki, GCPs, applicable privacy standards, or any condition of the study imposed by the IRB/EC, the Sponsor or their authorized representative may immediately secure compliance, discontinue further shipments of the study devices and/or seize unused devices on-site. An inability to secure compliance and/or to complete an investigation into the factors that are inhibiting compliance may result in the Investigator's termination from the study by the Sponsor.

Study close-out visits will be conducted after the final follow-up visit is completed at each site. Following the resolution of any outstanding data discrepancies and adverse events, the remaining study devices will be collected and returned to the Sponsor. A final study report will be generated and submitted to the Investigator and the appropriate study oversight authorities. Study document retention requirements will be reviewed with each site during the close-out visit.

